- In addition, at 6-month follow-up, the structured interview will also include questions to assess participant costs related to the intervention (e.g. transportation), food utilization (e.g. sharing, waste), barriers to intervention use, and program satisfaction among intervention participants, and use of free food resources (not including POH) among control and intervention participants.

b) Anthropometric assessments (baseline and 6 months). Anthropometry will be assessed by trained UCSF RAs at the same time as the structured interview, except when interviews are conducted by phone due to COVID. During COVID, UCSF staff may schedule anthropometric assessments separately from structured interviews to reduce exposure between staff and participants and will follow COVID safety guidelines for research (e.g. using personal protective equipment). UCSF RAs trained by clinicians in anthropometry will obtain three repeated measurements of weight (kg), height (cm), and waist and hip

- circumferences (cm). Tanita WB-800H portable digital scales will be used to measure the weight, SECA-213 stadiometer will be used to measure the height. For wheelchair-bound individuals RA will conduct anthropometry at a clinic with a wheelchair-accessible scale and stadiometer. At baseline and six months, all participants will undergo anthropometry
- c) Blood pressure assessments (baseline and 6 months). Blood pressure (BP) will be assessed by trained UCSF RAs at the same time as the anthropometry. BP will be measured using the Omron HEM 907XL IntelliSense Professional Digital Blood Pressure Monitor. Three blood pressure measurements will be taken after three to five minutes of inactivity and averaged to obtain a more accurate measure. At baseline and six months, all participants will undergo blood pressure measurements; at twelve months, blood pressure will be assessed in the intervention arm only.

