8. Health-related quality of life (HRQL). The standardized 12-item short form health survey will be used to measure the HRQL. The SF-12v2 provides a summary score for physical and mental health. The transformed *T* score has a mean=50 and SD=10, in which higher values means better health. The change in SF-12 *T* scores from baseline to six months by study arm will be reported
9. Body Mass Index (BMI). The average of three repeated measurements of weight and height will be obtained at baseline and at six months. The BMI will be calculated (weight (kg)/ (height (m)). Changes in in BMI values (kg/ m^2) from baseline to six months by study arm will be reported.
10. Diet quality. Dietary information using an automated self- administered 24-hour dietary recall instrument from the National Cancer Institute's (ASA24) will be collected. The HEI-2015 is a measure of diet quality which evaluates how well the food consumed aligns with the Dietary guidelines for American population. The HEI-2015 score ranges from 0-100 in which a higher score indicates better diet quality. The adequacy component of the HEI ranges from 0-60 and the moderation component ranges from 0-40 (both with higher score indicating better diet quality). Changes in the adequacy and moderation HEI-2015 scores from baseline to

six months by study arm will be reported.

11. Depressive symptoms. Symptoms corresponding to the Diagnostic and Statistical Manual of Mental Disorders will be measured using the 9-item Patient Health Questionnaire (PHQ-9), a reliable and valid measure of symptom severity. The PHQ-9 score ranges from 0 to 27, with higher scores indicating higher levels of depression. The change in PHQ-9 scores from baseline to six months among by study arms will be reported.
12. Diabetes distress scale. The diabetes distress scale (DDS) has 17 items measuring frustration, anger, and discouragement associated with managing complex diabetes healthcare directives. The DDS score ranges from 1 to 6, with higher scores indicating higher levels of distress. The change in diabetes distress scores from baseline to six months by study arms will be reported.

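### BMI change appears to use a height re-measured at six months, which adds avoidable noise; using baseline height at both visits gives a small, free gain in precision

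*Combined protocol and SAP*

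**What the plan says.** The combined protocol and SAP lists BMI as secondary outcome 9 (Section 6, 1) Outcome definitions): "The average of three repeated measurements of weight and height will be obtained at baseline and at six months". BMI is weight in kilograms divided by the square of height in metres, and the reported quantity is the change from baseline to six months by arm.

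Section 3, Data collection, b) Anthropometric assessments, confirms that height is taken again. Trained staff "will obtain three repeated measurements of weight (kg), height (cm), and waist and hip" circumferences, and "At baseline and six months, all participants will undergo anthropometry". One stadiometer model is named: "SECA-213 stadiometer will be used to measure the height".

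Section 6, 2) Analysis methods, regresses change on the baseline value and arm for the primary outcome and extends similar models to secondary outcomes. Section 2, Objectives, and the Aim 2 analyses name BMI as an intermediate outcome on the nutritional path.

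No sentence says which visit's height is the denominator at six months, and none fixes height at one value per participant.

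**The concern.** If each visit's weight is divided by the square of that visit's height, BMI change contains two height errors as well as the change in weight. Adults do not grow or shrink meaningfully in six months, so the height part is almost all error. Averaging three readings reduces independent reading error, but not an error shared by the whole visit. Visits may differ in setting: anthropometry is normally done with the interview, which may take place at the food provider's offices, a clinic, a community space or the home, and it may also be scheduled separately.

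What is at stake is precision on one secondary outcome. BMI is the only body-size measure in the outcome list, since weight is not an outcome in its own right. As an Aim 2 mediator, BMI measured with extra random error also has its path to the clinical outcome pulled somewhat toward zero.

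**Working it through.** **The plan's own figure.** There is none for BMI: no SD, effect size or power. The stated sample size of 98 per arm is for HbA1c change. It reproduces as 2 × (1.645 + 0.842)² × 1.3937² / 0.5² ≈ 96.1, so 97 per arm, but it has no bearing here.

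**Assumptions (not in the documents).** Mean BMI 33 kg/m²; mean height 1.65 m; true SD of BMI change 1.3 or 1.5 kg/m²; SD of the error in a visit's mean height, s, of 0.3, 0.5 or 1.0 cm, independent between visits.

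**Size of one error.** For small errors, error in BMI ≈ 2 × BMI / height × error in height = 2 × 33 / 1.65 = 40 kg/m² per metre, or 0.40 kg/m² per cm. Exact check at 90 kg: 90/1.65² = 33.06 and 90/1.66² = 32.66, a difference of 0.40 kg/m². That equals about 1.1 kg of weight.

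**Noise in the change.** Two independent visits contribute, so the SD of the noise is √2 × 0.40 × s (s in cm). Variance inflation is (noise SD / SD of change)².

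| s (cm) | Noise SD in BMI change (kg/m²) | Inflation, SD 1.3 | Inflation, SD 1.5 |
|---|---|---|---|
| 0.3 | 0.17 | 1.7% | 1.3% |
| 0.5 | 0.28 | 4.7% | 3.6% |
| 1.0 | 0.57 | 18.9% | 14.2% |

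**Effect on the arm comparison.** The planned model (change on baseline value and arm) was simulated 4,000 times per scenario. Further assumptions: 125 and 100 participants followed up (156 and 125 less 20%), SD of change 1.5, true difference 0.5 kg/m² in favour of the intervention (−0.5), two-sided 0.05, between-person SDs of 7 kg/m² for BMI and 0.09 m for height.

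| s (cm) | SE, height re-measured | Power, height re-measured | SE, baseline height | Power, baseline height |
|---|---|---|---|---|
| 0 | 0.201 | 69% | 0.201 | 69% |
| 0.5 | 0.205 | 67% | 0.201 | 69% |
| 1.0 | 0.216 | 62% | 0.201 | 69% |

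The mean estimate was between −0.495 and −0.496 in every scenario, with or without height error. Random height error therefore costs precision and does not bias the difference.

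**Effect on mediation.** In a simple linear model the mediator-to-outcome path shrinks by 1 − 1/(1 + inflation). That is 1.3% to 1.7% at 0.3 cm, 3.4% to 4.5% at 0.5 cm and 12.5% to 15.9% at 1.0 cm.

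**What remains with one height.** With baseline height at both visits, BMI change is weight change divided by baseline height squared. An error of 1 cm then only rescales the change by about 2 × 0.01 / 1.65 = 1.2%, which is negligible.

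**The case against.** Same-visit weight over same-visit height squared is a valid BMI, and the plan controls height measurement reasonably well: clinician-trained staff, a named stadiometer, three readings, and, where height is hard to take, an explicit provision: "For wheelchair-bound individuals RA will conduct anthropometry at a clinic with a wheelchair-accessible scale and stadiometer". The analyst is also to inspect outcomes and mediators for unusual values. With such controls a per-visit error SD near 1 cm may be pessimistic, and at 0.3 to 0.5 cm the loss is slight. All of this stands, and it is why the point is small.

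The text also does not say that the six-month height is the denominator. That is the natural reading, not an express statement. If something else is intended, the same clarifying sentence is needed.

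A reader might infer three stronger things, none of which the documents support:

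- **That the error itself is squared.** Height is squared; a small relative error in height is about doubled.
- **That the treatment effect on BMI is biased.** This would need height error to differ by arm, and nothing in the plan suggests that it does.
- **That participants with a six-month weight but no height will be lost.** Weight and height are planned for one session, so this is probably uncommon. The missing-data section allows multiple imputation for incomplete items. It is worded for questions, so whether it covers a missing height is unclear. As illustration only, 2% or 5% of 225 followed participants would be about 5 or 11 people.

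**Conclusion.** The concern holds as a minor inefficiency in how BMI change is derived. On the plain reading, height error from both visits enters the outcome although height carries no information about six-month change. The likely cost is about 1% to 5% in the variance of BMI change for a height error SD of 0.3 to 0.5 cm, rising to about 14% to 19% at 1.0 cm, with attenuation of similar size in the Aim 2 path through BMI. These figures rest on the assumed BMI, height, SD of change and error SDs above; none is in the documents. The arm comparison is unbiased, and the two primary outcomes are not touched. It is worth changing because the better derivation is free, not because the planned one would mislead.

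**What to change.** Add one sentence to secondary outcome 9: BMI at baseline and at six months is calculated with the participant's baseline height, taken as the mean of the three baseline readings. BMI change then reflects weight change only. A six-month weight without a height also stays usable: the intention-to-treat set requires completed baseline assessments, so a baseline height should exist for essentially everyone in it.

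Use the six-month height only as a check that flags possible recording errors in the baseline height. Averaging the two visits' heights is a less attractive alternative, because baseline BMI, which is both a baseline-table variable and the covariate in the model, would then depend on a measurement made after randomization.

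The cost is one line of SAP text and one line of derivation code. No new data are needed, and no other outcome changes.

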## 2) Analysis methods

- a. **Preliminary/Descriptive analyses.** Frequency tables for all variables and measures of central tendency and variability for continuous variables will characterize the sample and be stratified by randomization arm to check for non-equivalence. If the two arms differ at baseline on any covariates, the Rubin causal model (e.g., propensity scores, double- robust estimation) will be used to obtain the desired marginal effect estimates under the counterfactual assumption of balanced arm. Although the computerized data collection protocol and the presence of an interviewer should minimize missing data, the analyst will examine patterns of non-response, and inspect distributions of mediating and outcome variables to identify outlying or unusual values and assess distributional characteristics. Validity and reliability of scale constructs via confirmatory factor analysis and internal consistency will be verified.

**Analyses for Aim 1 (Diabetes and other clinical health outcomes):** The intervention is intended to improve clinical outcomes suggested by our intervention model. Specifically, the hypothesis is that the CHEFS-DM intervention will lead to improved (i.e., lower) mean HbA1c (primary outcome). For the primary analysis,

an intent-to-treat analysis of covariance will be done using the Stata regress and/or sem procedure with the primary outcome being changes from baseline to six months. The data for this analysis will be constructed in wide form, i.e., with an individual being a row in the data and the columns being the variables from both baseline and six months. The model will regress the change in an outcome variable on the baseline value of that outcome and arm (intervention or control). The model will be estimated by least-squares when using the regress procedure. Additional analyses will be done to a) check robustness if the two arms differ at baseline by controlling for the propensity score (or the covariates that were important in the propensity score); and b) adjust for medication use. If covariates have missing data, the sem procedure will be used with full information maximum likelihood to incorporate all covariate data under the assumption that missingness is at random.

For a secondary analysis, an intent-to-treat analysis will be performed using the Stata mixed procedure assessing whether the intervention resulted in differentially improved changes from baseline to six months in the primary outcome. The model will specify mixed (i.e., fixed and random) effects, be estimated by maximum likelihood, use all the longitudinal data, and account for variability among and within individuals using an exchangeable covariance structure. The fixed effects specified will be arm (intervention or control), visit (baseline or six months), and their interaction as a product term. The random effect will be individuals. The model is equivalent to a repeated-measures or differences-indifferences model. A fully fixed- effects model (with individuals as a fixed rather than random effect) will be examined as a robustness check.

Similar analyses will be done for the secondary outcomes using linear or logistic models as appropriate. For primary and secondary outcomes, Box-Cox transformations will be used to correct for skewness if needed.

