#### 4) Randomization

281 participants were randomized 1:1 to the intervention and control arms,

stratified by county (San Francisco vs. Alameda County) and poor diabetes control (A1c < 9%, vs.  $\geq$  9%). Details of the randomization and stratification method is stored securely in REDCap. Randomization based on a computer-generated assignment will occur after the participant has provided informed consent and completed baseline assessments.

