## Section 6: Analysis

### 1) **Outcome definitions**

Primary Outcome Measures:

1. Hemoglobin A1c. At baseline and six months, all participants will undergo the blood draw; at twelve months, the blood draw will be implemented in the intervention arm only. The change on HbA1c from baseline to six months by study arm will be reported.
2. Food security. Food insecurity will be measured with the adult version of the USDA Household Food Security Survey Module (HFSSM), validated in many populations. The score ranges from 0 to 10 . Higher scores indicates higher severity of food insecurity. The change in the food insecurity scores from baseline to six months by study arms will be reported.

Secondary Outcome Measures:

1. Glucose control. The change in the proportion of participants with glucose control, defined as HbA1c <9%, from baseline to six months by study arms will be reported.
2. Low food security. Food security as a binary response will be assessed, identifying a participant having low or very low food security or food security (food security or marginal food secure) by study arm.

3. Systolic and diastolic blood pressure. Changes in the average of three repeated measurements of systolic and diastolic blood pressure (mmHg) from baseline to six months by study arm will be reported.
4. Medication adherence. A Single-Item Rating Visual Analogue Scale (range 0-100) for medication adherence will estimate the percentage of medications taken in the past month and is reliable and valid, including in low-literacy populations. The change in medication adherence (percentage points) from baseline to six months between intervention and control arms will be reported.
5. Acute care utilization. Information on acute care utilization (emergency department and urgent care) by self-report and/or medical record review will be collected. The proportion of participants that used acute health care from baseline to six months by study arm will be reported.
6. Hospitalization. Information on hospital admissions will be collected by self-report and/or medical record review. The proportion of participants with at least one event of hospitalization will be reported by study arm.
7. Missed outpatient visits. Information on missed outpatient visits will be collected by self-report and/or medical record review. The proportion of participants that missed at least one outpatient visits from baseline to six months will be reported.

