### 4) Subgroup analysis

- a. Additional models and statistical interactions (i.e., product terms) will be performed to identify characteristics of individuals who most benefitted from the intervention, such as East Bay versus San Francisco, sex, race/ethnicity, food insecurity, poor T2DM control ( $A1c \geq 9$ ), and insulin use.

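### The primary ANCOVA and the mixed model leave out the randomisation strata, and an undefined imbalance trigger blurs the standing of propensity adjustment beside the ANCOVA

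*Combined protocol and SAP*

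**What the plan says.** **Randomisation.** Section 3, 4) Randomization, allocates 1:1, "stratified by county (San Francisco vs. Alameda County) and poor diabetes control", split at an A1c of 9%. The details of the method are held in REDCap and are not in the document. Section 7 gives 156 intervention and 125 control participants.

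**Primary model.** Section 6, 2) Analysis methods, Aim 1: "The model will regress the change in an outcome variable on the baseline value of that outcome and arm (intervention or control"). Secondary and intermediate outcomes follow the same form with linear or logistic models.

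**Mixed model (secondary analysis).** "The fixed effects specified will be arm (intervention or control), visit (baseline or six months), and their interaction as a product term". There is a random effect for individual, and a version "with individuals as a fixed rather than random effect) will be examined as a robustness check".

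**Outcomes.** Section 6, 1) Outcome definitions, lists two primary outcomes, HbA1c and food security. For the second, "Food insecurity will be measured with the adult version of the USDA Household Food Security Survey Module (HFSSM").

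**Where the strata return.** Only in Section 6, 4) Subgroup analysis, as product terms for characteristics "such as East Bay versus San Francisco, sex, race/ethnicity, food insecurity, poor T2DM control" and others.

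**Propensity adjustment.** It appears twice in Section 6, 2). The preliminary paragraph says that, if the arms differ on any covariate, propensity or double-robust methods "will be used to obtain the desired marginal effect estimates under the counterfactual assumption of balanced arm". The Aim 1 paragraph says "Additional analyses will be done to a) check robustness if the two arms differ at baseline by controlling for the propensity score", or for the covariates that mattered in it. Neither place gives a covariate list or a cut-off. Section 5, 5) lists the baseline characteristics and excludes significance tests on them.

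**The concern.** **Strata.** Stratified randomisation balances the arms on county and A1c stratum. A model without those factors leaves their variation in the residual, so if they predict outcome the reported standard error is too large and some power is lost. For HbA1c, continuous baseline HbA1c carries most of the A1c stratum, so mainly county is missing. For food insecurity, blood pressure, distress and the rest, both factors are missing. Neither the subgroup models nor the fixed-effects check fills the gap. Product terms estimate differences in effect, not one stratum-adjusted overall effect. Individual fixed effects remove stratum differences in level but not in change.

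**Propensity trigger.** The plan names the ANCOVA as primary in Section 6, 2) and again in Section 7. The preliminary sentence nevertheless describes the propensity estimate as the one desired, on a condition judged after looking at baseline data. A reader cannot tell in advance whether that estimate will be produced, or what standing it will have beside the ANCOVA.

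**Medication use.** A smaller point: one additional analysis adjusts for medication use without saying when it is measured, and the inventory is taken at both baseline and 6 months.

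**Working it through.** **Inputs from the documents.** SD of change 1.3937, difference 0.5, one-sided alpha 0.05, 98 per arm, 20% attrition, and a detectable food-insecurity difference of 1.3 points (Section 3, 5); arms of 156 and 125 (Section 7); 23 baseline characteristics, counted from Section 5, 5).

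**Assumptions.** The documents give no stratum effects. I take county effects b = 0.2, 0.4 and 0.6 residual SD with a 50:50 county split, and a 30:70 split for the A1c stratum.

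**1. The plan's own figure.** The two-sample calculation with these inputs needs 97 per arm (noncentral t power 0.801), against the stated 98 (power 0.804). With attrition, 196/0.80 = 245, as stated. The sample size reproduces and need not change.

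**2. SE without county, relative to SE with it.** Ratio = √(1 + b²p(1−p)). At p = 0.5:
- b = 0.2: √1.01 = 1.005
- b = 0.4: √1.04 = 1.020
- b = 0.6: √1.09 = 1.044

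Simulation with 281 randomised at 156:125, balanced within the four strata, 80% retained, and both strata added to the model gives about 1.004, 1.019 and 1.043. With b = 0 it gives 0.999, so strata that predict nothing cost about 0.1% of SE. If allocation had not been balanced within strata, the b = 0 ratio would be 0.995, a cost of about 0.5%.

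**3. Power for HbA1c.** Completers: 0.8 × 156 ≈ 125 and 0.8 × 125 = 100. For a difference of 0.5, one-sided 0.05, dividing the SD of 1.3937 by the ratios from the formula:

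| County effect (residual SD) | Power |
|---|---|
| county not in model | 0.846 |
| 0.2, county in model | 0.850 |
| 0.4, county in model | 0.859 |
| 0.6, county in model | 0.873 |

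An effect of 0.4 SD is 0.4 × 1.3937 = 0.56 HbA1c points, larger than the plan's minimum important difference of 0.5. The low end is therefore more plausible.

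**4. Food insecurity and the A1c stratum.** Solving 80% power for 1.3 points at 98 per arm, one-sided, gives an SD of change of about 3.65. An A1c-stratum effect of 0.2 SD is 0.7 points and of 0.4 SD is 1.5 points. At 30:70 the ratios are √(1 + 0.04 × 0.21) = 1.004 and √(1 + 0.16 × 0.21) = 1.017. Since 1.5 exceeds the 1.3-point detectable difference, the low end is again more plausible.

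**5. Mixed model.** With complete two-visit data the arm-by-visit estimate is the difference between arms in mean change. Stratum main effects cancel from it; only stratum-by-visit terms adjust it.

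**6. How often the trigger fires by chance.** SE of a standardised mean difference (SMD) = √(1/156 + 1/125) = 0.120. For one covariate, P(|SMD| > 0.1) = 0.405 and P(|SMD| > 0.2) = 0.096. For at least one of 23 independent covariates, 1 − (1 − 0.096)²³ ≈ 0.90. Over between-covariate correlations from 0.4 to 0:

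| Cut-off | At least one of 23 differs |
|---|---|
| \|SMD\| > 0.1 | over 99% |
| \|SMD\| > 0.2 | 76–90% |
| \|SMD\| > 0.25 | 42–58% |

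**7. Odds ratios.** For the plan's example of 0.36 versus 0.20, the marginal OR is (0.20/0.80)/(0.36/0.64) = 0.444. With an evenly split stratum of assumed OR 1.65 or 7.4, the conditional OR giving the same margins is 0.440 or 0.384. Adding strata to a logistic model therefore changes what the odds ratio means.

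**The case against.** The strongest reply is that little is at stake. Stratified 1:1 allocation makes the unadjusted linear estimate unbiased and its standard error, if anything, conservative. The baseline value of each outcome is in the ANCOVA, so only a stratum effect beyond baseline counts, and at 0.2 SD that is under half a percent of SE. This stands and sets the weight of the point. It does not remove it, because the terms are already recorded and cost almost nothing to add.

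On propensity adjustment, the plan twice names the ANCOVA as primary, and the preliminary sentence can be read as a general statement that the Aim 1 paragraph then makes specific. That also largely stands. What survives is a written rule with no cut-off that would often fire by chance. The link to the 23 characteristics is my assumption, since the preliminary paragraph does not define its covariates.

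Three stronger readings are tempting and not supported:
- **Bias from 156:125.** A reader might infer that allocation ratios differed between counties. No section says so, the method is not described, and a chance imbalance is not bias.
- **A replaced primary analysis.** The documents do not say that the propensity estimate supplants the ANCOVA.
- **A p < 0.05 trigger.** Section 5, 5) excludes significance tests on baseline characteristics, so that cut-off should not be attributed to the plan.

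**Conclusion.** The concern holds as a minor one. The omission of the strata is a matter of text and is certain. Its effect is a small loss of precision, not bias: about 0.4% of SE at the more plausible low end and 4.3% at the high end of the assumed county effects, with HbA1c power rising from 0.846 to between 0.850 and 0.873 once county is included. These sizes rest on assumed stratum effects, an even county split and 20% attrition. A reader should not take the omission as a threat to the validity of the HbA1c comparison.

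The propensity wording leaves two roles unreconciled. Depending on the meaning of a baseline difference, the rule would fire in somewhere between about two-fifths and nearly all correctly randomised trials of this size. It should not depend on observed balance.

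**What to change.** 1. **ANCOVA.** Before outcome data by arm are seen, add county and A1c stratum, as recorded at randomisation, for HbA1c, food insecurity and the continuous secondary outcomes. For HbA1c, at least add county beside continuous baseline HbA1c. Use the recorded stratum: the data-collection section takes diabetes control status from the latest medical-record value, which may differ from the study draw. If outcome data by arm have been seen, keep the stated ANCOVA and report the stratum-adjusted model as a labelled sensitivity analysis.
2. **Mixed model.** Add county-by-visit and A1c-stratum-by-visit terms.
3. **Logistic models.** Add the strata and name the odds ratio as conditional, or report a standardised marginal effect with its 95% interval.
4. **Propensity step.** State that the ANCOVA is the primary result whatever the observed balance. Replace both conditional sentences with one propensity- or covariate-adjusted sensitivity analysis on a covariate list fixed in advance and run regardless.
5. **Medication use.** Adjust for baseline use, or label an analysis with 6-month use as adjusting for a post-randomisation variable.

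**Cost.** SAP wording and two model terms. If the strata predict nothing, the SE widens by about 0.1% under within-stratum balance, and by up to about 0.5% without it. Timing is the real constraint: version 2 is dated 02/05/2025 and analysis was due to begin in March 2025.
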